9.1.2 Safety

There are no primary objectives for safety.

9.1.3 Efficacy

There are no primary objectives for efficacy.

9.2 Secondary Endpoints and Assessment Methods

9.2.1 Immunogenicity

9.2.1.1 Immunogenicity Endpoints

Gardasil immunogenicity:

• Seroconversion against each Gardasil HPV antigen (HPV-6, HPV-11, HPV-16, HPV-18) 28 days after each dose of Gardasil

Seroconversion is defined as changing serostatus from seronegative at baseline to seropositive (> lower limit of quantitation [LLOQ] of the assay) or \geq 4-fold rise in Ab titer if seropositive at baseline.

• Ab levels (measured by cLIA) against each Gardasil HPV antigen (HPV-6, HPV-11, HPV-16, HPV-18) at baseline and after each dose of Gardasil

CYD dengue vaccine immunogenicity:

• Neutralizing Ab titers against each of the four parental dengue virus serotypes of the CYD dengue vaccine as determined by PRNT50 at baseline and after each dose of the CYD dengue vaccine

- Neutralizing Ab titers ≥ 10 (1/dil) against each of the four and against at least 1, 2, 3, or 4 parental dengue virus serotypes of the CYD dengue vaccine as determined by PRNT50at baseline and after each dose of the CYD dengue vaccine
- Neutralizing Ab titers ≥ different titer thresholds (1/dil) against each parental dengue virus serotype of the CYD dengue vaccine as determined by PRNT50 at baseline and after each dose of the CYD dengue vaccine

9.2.1.2 Immunogenicity Assessment Methods

The immunogenicity assessment methods for the secondary endpoints are the same as those presented in Section 9.1.1.2.

9.2.2 Safety

9.2.2.1 Safety Definitions

The following definitions are taken from the ICH E2A Guideline for Clinical Safety Data Management: Definitions and Standards for Expedited Reporting.

Adverse Event:

An AE is any untoward medical occurrence in a patient or clinical investigation subject administered a pharmaceutical product and which does not necessarily have to have a causal relationship with this treatment. An AE can therefore be any unfavorable and unintended sign (including an abnormal laboratory finding, for example), symptom or disease temporally associated with the use of a medicinal product, whether or not considered related to the medicinal product.

Therefore an AE may be:

- A new illness
- The worsening of a concomitant illness
- An effect of the vaccination, including the comparator
- A combination of the above
- All AEs include serious and non-serious AEs.
- Surgical procedures are not AEs; they are the action taken to treat a medical condition. It is the condition leading to the action taken that is the AE (if it occurs during the trial period).

Pre-existing medical conditions are not to be reported as AEs. However, if a pre-existing condition worsens in frequency or intensity, or if in the assessment of the treating physician there is a change in its clinical significance, this change should be reported as an AE (exacerbation). This applies equally to recurring episodes of pre-existing conditions (e.g., asthma) if the frequency or intensity increases post-vaccination.

Serious Adverse Event:

Serious and *severe* are not synonymous. The term *severe* is often used to describe the intensity of a specific event as corresponding to Grade 3. This is not the same as *serious* which is based on

patient/event outcome or action criteria usually associated with events that pose a threat to a patient's life or functioning. Seriousness, not severity, serves as a guide for defining regulatory reporting obligations.

An SAE is any untoward medical occurrence that at any dose:

- Results in death
- Is life-threatening^a
- Requires inpatient hospitalization or prolongation of existing hospitalization^b
- Results in persistent or significant disability/incapacity^c
- Is a congenital anomaly/birth defect
- Is an important medical event^d

Additionally, the following important medical events are to be considered as SAEs and reported to the Sponsor according to the procedure described in Section 10:

Adverse Reaction:

All noxious and unintended responses to a medicinal product related to any dose should be considered adverse reactions (AR).

(The phrase "responses to a medicinal product" means that a causal relationship between a medicinal product and an AE is at least a reasonable possibility)

Unexpected Adverse Reaction (UAR):

An UAR is an AR, the nature or severity of which is not consistent with the applicable product information (e.g., Investigator's Brochure for an unapproved investigational medicinal product).

The following additional definitions are used by Sanofi Pasteur:

^a The term "life-threatening" refers to an event in which the subject was at risk of death at the time of the event; it does not refer to an event which hypothetically might have caused death if it were more severe.

^b All medical events leading to hospitalizations will be recorded and reported as SAEs, with the exception of: hospitalization planned before inclusion into the study or out-patient treatment with no hospitalization.

^c "Persistent or significant disability or incapacity" means that there is a substantial disruption of a person's ability to carry out normal life functions.

^d Medical and scientific judgment should be exercised in deciding whether expedited reporting is appropriate in other situations, such as important medical events that may not be immediately life-threatening or result in death or hospitalization but may jeopardize the health of the subject or may require intervention to prevent one of the other outcomes listed in the definition above. These should also usually be considered serious. Examples of such events include allergic bronchospasm requiring intensive treatment in an emergency room or at home, blood dyscrasias or convulsions that do not result in inpatient hospitalization, or the development of drug dependency or drug abuse, new onset diabetes, or autoimmune disease.

Solicited Reaction:

- 4) A solicited reaction is an event that is prelisted in the CRF. The assessment of these AEs post-vaccination is mandatory. A solicited reaction is defined by a combination of:
- Symptom and
- Onset post-vaccination
- e.g., injection site pain between D0 and D7 post-vaccination, or headache between D0 and D14.

A solicited reaction is therefore an AR observed and reported under the conditions (symptom and onset) prelisted (i.e., solicited) in the CRF and considered as related to vaccination.

Unsolicited AE/AR:

An unsolicited AE is an observed AE that does not fulfill the conditions prelisted in the CRF in terms of diagnosis and/or onset post-vaccination, i.e., excluding solicited reactions, e.g., if headache between D0 and D14 is a solicited reaction (i.e., prelisted in the CRF), then a headache starting on D14 is a solicited reaction, whereas headache starting on D15 post-vaccination is an unsolicited AE.

An unsolicited non-serious AE is an unsolicited AE excluding SAEs.

Injection Site Reaction:

An injection site reaction^a is an AR at and around the injection site. Injection site reactions are commonly inflammatory reactions.

Systemic AE:

Systemic AEs are all AEs that are not injection site reactions. They therefore include systemic manifestations such as headache, fever, as well as localized or topical manifestations that are not associated with the vaccination site, e.g., erythema that is localized but that is not at the injection site.

Adverse Events of Special Interest (AESIs):

AEs of special interest are AEs that are considered by the Sponsor to be relevant for the monitoring of the safety profile of the investigational vaccine.

^a All injection site AEs are considered to be related to vaccination and are therefore all *injection site reactions*.

9.2.2.2 Safety Endpoints

Safety endpoints for Gardasil and CYD dengue vaccine safety in each group are:

- Occurrence of immediate AEs reported within 30 minutes after each and any injection
- Occurrence of solicited (i.e., pre-listed in the subject's diary card [DC] and electronic case report form [CRF]) injection site reactions (pain, erythema, and swelling) occurring up to 7 days after each and any injection
- Occurrence of solicited systemic reactions (fever, headache, malaise, myalgia, and asthenia) occurring up to 14 days after each and any injection
- Occurrence of unsolicited AEs occurring up to 28 days after each and any injection
- Occurrence of non-serious AESIs* occurring within 7 days following each and any injection
- Occurrence of SAEs, including serious AESIs* (with specific time windows according to the type of AESI*) throughout the trial
- Occurrence of hospitalized VCD cases throughout the trial (i.e., from D0 through end of the study)
- * Hypersensitivity/allergic reactions (serious or not) within 7 days after each CYD dengue vaccine injection, serious viscerotropic disease within 30 days after each CYD dengue vaccine injection, serious neurotropic disease within 30 days after each CYD dengue vaccine injection; serious dengue cases requiring hospitalization (i.e., hospitalized suspected dengue case) occurring in all subjects at any time during the study.

Depending on the item, these could include: nature (Medical Dictionary for Regulatory Activities [MedDRA] preferred term), time of onset, duration, number of days of occurrence, grade of severity, relationship to vaccine, action taken, whether the event/reaction led to early termination from the study, seriousness, or outcome.

Hospitalized suspected dengue case is defined as an acute febrile illness with diagnosis of dengue requiring hospitalization (with bed attribution). In such cases, 1 unplanned acute blood sample (within the first 5 days after fever onset) will be collected for virological confirmation of hospitalized suspected dengue case. A suspected case will be considered VCD if there is a detection of WT dengue virus by dengue NS1 Ag ELISA and/or dengue RT-PCRs (at the GCI or GCI designated laboratory).

Note: Acute blood sample for all hospitalized suspected dengue cases should be collected within the pre-specified timeframe as described above. If this cannot be accomplished, this sample should still be obtained as soon as possible thereafter, for IDMC severity assessment.

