Dengue unexposed subjects (seronegative, See Section 9.1.1.1 for definition) at baseline will not receive further dengue vaccine injection. If they consent to continue their participation in the study, they will be contacted by phone call for a safety follow-up 6 months after the last injection. They will not attend any further study visits, except the unscheduled visit and/or the next schedule visit planned to sign the AF and ICF during which they will be proposed to have a blood sample for the assessment of HPV antibodies after the 2 doses of Gardasil.

For dengue exposed subjects who consent to continue in the study and receive the CYD dengue vaccine injection(s), procedures will be as follows:

Vaccinations

Subject will receive a total of 5 injections, i.e., 3 doses of the CYD dengue vaccine and 2 doses of Gardasil administered either concomitantly (Group 1) or sequentially (Group 2), according to the following schedule:

- **Group 1**: Gardasil and the CYD dengue vaccine (concomitantly) at Day (D)0 and Month (M)6, and CYD dengue vaccine (alone) at M12
- **Group 2**: Gardasil (alone) at D0 and M6, and the CYD dengue vaccine (alone) at D0+28D (M1), M1+6 months (M7), and M1+12 months (M13)

Study Visits

Subjects will have to attend 6 (Group 1) or 8 (Group 2) visits and will have 1 phone call for the 6month follow-up after the last injection of the CYD dengue vaccine. Interim phone calls will be given 7 days after each injection and 2 months after blood samples during the 6-month period after each vaccination.

An unscheduled visit and/or phone call will take place during the study pause in order to communicate the new data on the CYD dengue vaccine to each subject. This visit will be either before or at the time of the next visit initially planned (V05, V06 or V07, depending on study progression). A "Dear Patient Letter" approved by IEC/IRB will be explained to the subjects to share with them the new safety data. Dengue serostatus at baseline may be communicated to the subjects at the time of this unscheduled visit if available.

Subject's participation in the study is expected to be of 18 or 19 months. Time for the approval of Protocol Amendment 1 by the competent authorities and completion of the associated logistic tasks will result into a hold of study activities of several months (approximately 2 months), and thus, to an extension of study duration for dengue exposed subjects.

Blood Samples

Subjects will provide blood samples:

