- 18) Remind the parent/legally acceptable representative to notify the site in case of an SAE.
- 19) Complete the relevant CRF pages for this visit.

Phone Call 1 (PC1) (7 days [+8 days] after Visit 1)

All subjects who received vaccination(s) will be contacted 7 days after vaccination(s). During this contact, the Investigator or designated study personnel will ask the subject or parent/legally acceptable representative if the subject has experienced any SAE, including hospitalized suspected dengue case, in the time since vaccination. If it did occur, follow the instructions for reporting it. The Investigator or designated study personnel will also remind the instructions to the parent/legally acceptable representative and to complete regularly the DC. A follow-up visit can be arranged depending on the info recorded during the phone call.

Visit 2 (Month 1; 28 [+14] days after Visit 1)

The Investigator or designated study personnel will:

- 1) Check the information entered into the DC by interviewing the subject/subject's parent (s)/legally acceptable representative(s) and request information concerning any medical event, serious or not, that may have occurred since Visit 1.
- 2) Perform a physical examination
- 3) Record the subject's axillary temperature (Group 2)

^a It is important to note that, if the attempt(s) to collect blood is (are) unsuccessful, the subject should be given the opportunity for another attempt, even on another day. If ultimately a blood sample cannot be obtained, the reason will be recorded in the CRF. In that case, and if the subject wants to participate in the trial, he/she will be vaccinated.

- 4) Collect information regarding the subject's medication status since the previous visit.
- 5) For female subjects of childbearing potential, perform a urine pregnancy test before injection (subjects in Group 2 only).
- 6) Obtain blood sample (see Section 7.1 for detailed instructions regarding the handling of blood samples).
- 7) Review temporary and definitive contraindications to vaccination (Group 2).
- 8) Inject the first dose of the CYD dengue vaccine to subjects randomized into Group 2.
- 9) Keep the subject under observation for 30 minutes, and record any immediate AE in the source document (Group 2).
- 10) Record the date of injection, the site and side of injection and the route of administration, as well as the dose number of the vaccine (Group 2).

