9.1 Primary Endpoints and Assessment Methods

9.1.1 Immunogenicity

9.1.1.1 Immunogenicity Endpoints

The primary endpoint(s) for the evaluation of immunogenicity are:

Gardasil immunogenicity

• Ab levels (measured by [cLIA]) against each Gardasil HPV antigen (HPV-6, HPV-11, HPV-16, HPV-18) 28 days after the last dose of Gardasil

CYD dengue vaccine immunogenicity

• Neutralizing Ab levels (measured by dengue plaque reduction neutralization test [PRNT50]) against each of the four parental dengue virus serotypes of the CYD dengue vaccine (1, 2, 3, 4) 28 days after the last dose of the CYD dengue vaccine

Definition of dengue serostatus

The dengue serostatus at baseline is defined as the presence of Abs against at least one dengue serotype in the baseline sample (by dengue 50% plaque reduction neutralization test [PRNT50) in the blood sample collected at V01 (BL1) from all subjects. The baseline dengue status variable will be calculated for each subject as follows:

- Dengue immune subjects (dengue exposed) at baseline are defined as those subjects with titers $\geq 10 (1/dil)$ for at least one serotype with the parental dengue virus strain
- Dengue non-immune subjects (dengue unexposed) at baseline are defined as those subjects with titers <10 (1/dil) (not quantified) for all serotypes with parental dengue virus strains with available "valid" results (i.e. different from missing or "NR")

The baseline dengue status will be set to missing when the titer for any serotypes with parental dengue virus is either missing or not quantified (except if all are not quantified in which case the dengue status is non-immune)."

In case of limited serum volume, the priority will be given to the testing of the dengue serostatus at baseline testing over the other testing (HPV immunogenicity post Gardasil may be not performed if not enough blood volume).

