Serial, two-fold dilutions of serum to be tested (previously heat-inactivated) are mixed with a constant challenge-dose of each dengue virus serotype 1, 2, 3 or 4 (expressed as plaque-forming unit [PFU]/mL). The mixtures are inoculated into wells of a microplate with confluent Vero cell monolayers. After adsorption, cell monolayers are incubated for a few days. The presence of dengue virus infected cells is indicated by formation of plaques. A reduction in virus infectivity due to neutralization by Ab present in serum samples is detected. The reported value (end point neutralization titer) represents the highest dilution of serum at which \geq 50% of dengue challenge virus (in plaque counts) is neutralized when compared to the mean viral plaque count in the negative control wells which represents the 100% virus load. The end point neutralization titers are presented as continuous values. The lower limit of quantitation (LLOQ) of the assay is 10 (1/dilution [dil]).

This assay will be performed on blood samples taken at V01 (Group 1 only), V02, V03 (Group 2 only), V05 (Group 1 only), V06 (Group 2 only), and V08.

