#### **4.4.5 Baseline Dengue status**

The dengue serostatus at baseline is defined as the presence of Abs against at least one dengue serotype in the baseline sample (by dengue 50% plaque reduction neutralization test [PRNT50]) in

the blood sample collected at V01 for group 1 and at V02 for group 2. The baseline dengue status will be derived for each subject as follows:

- Dengue immune subjects (seropositive) at baseline are defined as those subjects with titers  $\geq 10$  (1/dil) for at least one serotype with the parental dengue virus strain.
- Dengue non-immune subjects (seronegative) at baseline are defined as those subjects with titers  $< 10$  (1/dil) (not quantified) for all serotypes with parental dengue virus strains with available and “valid” results (i.e. not coded “NR”) in the serology database.
- Otherwise the baseline status will be classified as undetermined and subjects will have their dengue baseline status derived as non-immune.

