**Table 5.1: Descriptive statistics produced**

|   |  |  |
|---|--|--|
| Baseline characteristics and follow-up description | Categorical data                      | Number of subjects.
Percentage of subjects.   |
|   | Continuous data                       | Mean, standard deviation, quartiles, minimum, and maximum.   |
| Clinical safety results                            | Categorical data                      | Solicited: Number and percentage (95% confidence interval [CI]) of subjects and number of events
Unsolicited: Number and percentage (95% CIs) of subjects and number of events.
Hospitalized VCD cases: Number and percentage (95% CIs) of subjects                                      |
| Immunogenicity results                             | Categorical data (cutoff)             | Number and percentage (95% CIs) of subjects.   |
|   | Continuous data (titer / titer ratio) | $\log_{10}$ : Mean and standard deviation.
Anti- $\log_{10}$ (work on $\log_{10}$ distribution, and anti- $\log_{10}$ applied): Geometric mean, 95% CI of the geometric mean, quartiles, minimum, and maximum.
Graphical representation by Reverse Cumulative Distribution Curve (RCDC). |

The CI for the single proportion will be calculated using the exact binomial method (Clopper-Pearson method, quoted by Newcombe (1), i.e., using the inverse of the beta integral with SAS®).

For immunogenicity, assuming that  $\log_{10}$  transformation of the titers follows a normal distribution, at first, the mean and the 95% CI will be calculated on  $\log_{10}$  titers using the usual calculation for normal distribution (using Student's t distribution with n-1 degree of freedom), then antilog transformations will be applied to the results of calculations, in order to provide geometric means (GMs) and their 95% CI.

GM is defined as follows:

$$GM = \left( \prod_{i=1}^n y_i \right)^{1/n} = 10^{\hat{\left( \frac{1}{n} \sum_{i=1}^n \log_{10}(y_i) \right)}}$$

where  $(y_1, y_2, \dots, y_n)$  are the observed titers or other data where applicable for each subject.

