#### **5.2.3 Safety Analysis Set**

The SafAS is defined as those subjects who have received at least one dose of the study vaccines. All subjects will have their safety analyzed after each dose according to the vaccine they actually received, and after any dose according to the vaccine received at first dose.

The safety data will also be presented separately for dengue immune, non-immune / undetermined subjects.

Safety data recorded for a vaccine received out of the protocol design will be excluded from the analysis (and listed separately).

Note: Subject will be included in the “any dose” analysis according to the 1st dose received that corresponds to a protocol group.

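### Hospitalized dengue by baseline serostatus: a Group 2 case before the first CYD dose would be counted, and classified by a sample taken after the event (minor; one SAP sentence settles it)

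*Protocol*

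**What the plan says.** **Counting window.** Protocol 9.2.2.2 counts hospitalized VCD "cases throughout the trial (i.e., from D0 through end of the study", with no difference between groups. SAP 4.2 adopts the endpoint by reference.

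**First CYD dose.** Protocol 5.1.3 gives Group 2 Gardasil alone at Day 0 and Month 6, "and the CYD dengue vaccine (alone) at D0+28D (M1), M1+6 months (M7), and M1+12 months (M13". The gap before the first CYD dose follows from Protocol 5.1.4: "Visit 2 (Month 1; 28 [+14] days after Visit 1".

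**Baseline serostatus.** SAP 4.4.5 uses "the blood sample collected at V01 for group 1 and at V02 for group 2". A titer of at least 10 to one serotype makes a subject immune. An undetermined status is derived as non-immune.

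**A conflict inside the protocol.** Protocol 9.1.1.1 says serostatus is determined "in the blood sample collected at V01 (BL1) from all subjects". Protocol 9.1.1.2 does not plan that test in Group 2: "This assay will be performed on blood samples taken at V01 (Group 1 only), V02, V03 (Group 2 only". Table 7.1 likewise draws only the HPV sample in Group 2 at V01, and SAP 3.1 agrees with V02.

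**Display.** SAP Table 5.1 lists "Hospitalized VCD cases: Number and percentage (95% CIs) of subjects", without a start point. SAP 5.2.3 adds: "The safety data will also be presented separately for dengue immune, non-immune / undetermined subjects". Entry to the safety set needs one dose of either vaccine, so Group 2 enters at Day 0.

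**Early-event rule.** SAP 4.4.1.3.2 sets aside only SAEs with negative onset relative to the previous vaccination.

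**The concern.** A stratifying variable should be fixed before the events it stratifies. In Group 1 it is: sample, first CYD dose and start of counting coincide at V01. In Group 2 counting starts 28 to 42 days before the sample, and the event can change the result of the sample. The negative-onset rule does not help, because Gardasil at Day 0 makes any onset after that injection non-negative.

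The SAP's own wording adds an asymmetry. Section 5.1.2.2 assesses immune subjects after Gardasil or CYD doses, but non-immune subjects after CYD doses only. Read literally, a Group 2 case after the first Gardasil dose could be shown on the immune side and not on the other.

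At stake is the descriptive table closest to the reason for Amendment 1. It would hold events that cannot be effects of CYD, and with few cases expected, one such event shows.

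**Working it through.** **1. The plan's own durations.** Group 1: 12 + 6 = 18 months. Group 2: 1 + 12 + 6 = 19 months. Both agree with Protocol 5.1.5. The extra month in Group 2 is the period before CYD.

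**2. Length of that period.** From the V02 window, 28 to 28 + 14 = 42 days.
- Share of Group 2 follow-up: 28/(19 × 30.44) = 4.8%; 42/(19 × 30.44) = 7.3%.
- Person-years for 264 subjects: 264 × 28/365.25 = 20.2; 264 × 42/365.25 = 30.4.

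**3. Expected cases before CYD.** The documents give no incidence of hospitalized dengue in this population. I assume 0.2 to 1% per year.
- Lowest: 20.2 × 0.002 = 0.04. Highest: 30.4 × 0.01 = 0.30.
- Chance of at least one, 1 − exp(−expected): 4% to 26%.
- Whole trial at the same rates: 264 × 1.5 + 264 × 19/12 = 814 person-years, hence 1.6 to 8.1 cases. This takes full planned follow-up for everyone, so it is an approximation after Amendment 1.

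**4. How those cases would be labelled.** Let s be the share already seropositive at Day 0. The documents do not give it; the protocol synopsis says the number of exposed subjects is not known. I take 20%, 50% and 80%, with the risk of being a case unrelated to s. Let f be the share of onsets early enough for a positive titer at V02. With onsets spread evenly and antibody assumed detectable 7 to 10 days after onset:
- 28-day gap: f = 18/28 = 64% to 21/28 = 75%.
- 42-day gap: f = 32/42 = 76% to 35/42 = 83%.

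Proportion labelled immune = s + (1 − s)f. Proportion of those labels due to the counted infection = (1 − s)f / [s + (1 − s)f].

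| s | Labelled immune | Of these, due to the counted infection |
|---|---|---|
| 20% | 71–87% | 72–77% |
| 50% | 82–92% | 39–45% |
| 80% | 93–97% | 14–17% |

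The remaining 3 to 29% test negative at V02 and are placed in non-immune.

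**5. Cases with a wrong immune label.** Expected cases × (1 − s)f:
- Lowest: 0.0405 × 0.2 × 0.643 = 0.005.
- Highest: 0.304 × 0.8 × 0.833 = 0.20.

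**6. What one case does.** With an assumed 378 immune subjects, 3 cases are 0.79% (Clopper-Pearson 95% CI 0.16 to 2.30%) and 4 are 1.06% (0.29 to 2.69%). The change is visible, but the intervals largely overlap.

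**The case against.** **The protocol's analysis already avoids this.** Protocol 12.1.2.2 ties the serostatus-specific safety analysis to doses of CYD, and an event before V02 follows none. This stands for the protocol and supports the fix. It does not settle the SAP, whose sections 5.1.2.2, 5.2.3 and 5.2.5 are broader. Table 5.1 states neither window nor stratum, so a serostatus table counted from Day 0 is a reading of the SAP that nothing in it excludes, rather than an explicit instruction.

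**Counting from Day 0 is correct by randomized group.** It is: Gardasil is a study vaccine given on that day. Protocol 9.2.2.2 needs no change.

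**A V01 sample would cure the label.** Protocol 9.1.1.1, taken literally, would do so. It conflicts with the assay and sampling plan, and a case before any CYD dose would still stand in the serostatus table.

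**Such a case would be noticed.** Last vaccination and onset are derived for each SAE, and the IDMC reviews hospitalized VCD. True, but the SAP does not say how to tabulate the case once noticed.

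**Stronger readings a reader might infer, which the documents do not support:**
- *That the immune label normally results from the counted infection.* This needs a child seronegative at Day 0 and infected long enough before V02. At 80% seropositive it explains only 14 to 17% of the immune labels.
- *That the error runs only toward the immune stratum.* A recent onset may test negative, and an undetermined status is derived as non-immune.
- *That it dilutes a vaccine-related excess in non-immune subjects.* Both groups receive CYD, so there is no arm without dengue vaccine. After Amendment 1 non-immune subjects are followed to 6 months after their last injection, while immune subjects may continue through dose 3 plus 6 months. The crude percentages already rest on follow-up that differs by about six months.

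**Conclusion.** The concern holds as a minor gap in a descriptive table. In Group 2, VCD counting starts 28 to 42 days before the serostatus sample and first CYD dose, and no SAP rule keeps cases from that interval out of the serostatus display. Expected cases are well below one: 0.04 to 0.30 at assumed rates of 0.2 to 1% per year. Those wrongly labelled immune because of the counted infection number about 0.005 to 0.20, given the assumed detection lag and Day 0 seropositivity. The incidence, the lag and the seropositive share are all assumptions. The structural finding rests on none of them. The co-primary and secondary non-inferiority tests and the by-group VCD count are unaffected. The case for acting is that the rule costs almost nothing and spares a decision made after a case has been seen.

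**What to change.** **In the SAP** (4.4.1.4.6 or 5.1.2.2, with a note to Table 5.1): for hospitalized VCD by baseline dengue status, count from each subject's first CYD injection (V01 in Group 1, V02 in Group 2), with subjects who received at least one CYD dose as the denominator. List cases with onset before the first CYD injection separately. This brings the SAP into line with Protocol 12.1.2.2.

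**Leave as is:** the by-group count from Day 0 and Protocol 9.2.2.2.

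**Reconcile:** the V01 statement for all subjects in Protocol 9.1.1.1 with Protocol 7.1.1 (Table 7.1) and 9.1.1.2 and SAP 3.1 and 4.4.5, which place the Group 2 dengue baseline at V02.

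**Cost:** one sentence and a table note in the SAP, and one correction of wording in the protocol. Injection and onset dates are already collected, so no new data are needed.
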